8 TREATMENTS

The following is a list of the study treatment abbreviations and ordering that will be used in the TFLs for Part 1.

Study Treatment Name	Abbreviation	Treatment Order on TFLs
GDC-0134 F16 capsule fed (Test)	F16 fed	1
GDC-0134 F09 capsule fed (Reference)	F09 fed	2

The following is a list of the study treatment abbreviations and ordering that will be used in the TFLs for Part 2.

Study Treatment Name	Abbreviation	Treatment Order on TFLs
GDC-0134 F15 capsule fasted (Test)	F15 fasted	1
GDC-0134 F09 capsule fasted (Reference)	F09 fasted	2

The following is a list of the study treatment sequence abbreviations and ordering that will be used in the baseline TFLs for Part 1.

Study Treatment Sequence	Abbreviation	Treatment Order on TFLs
GDC-0134 F09 capsule fed (Reference)/	F09 fed/F16 fed	1
GDC-0134 F16 capsule fed (Test)	F16 fed/F09 fed	2
GDC-0134 F09 capsule fed (Reference)		

The following is a list of the study treatment sequence abbreviations and ordering that will be used in the baseline TFLs for Part 2.

Study Treatment Sequence	Abbreviation	Treatment Order on TFLs
GDC-0134 F09 capsule fasted (Reference)/ GDC-0134 F15 capsule fasted (Test)	F09 fasted/F15 fasted	1
GDC-0134 F15 capsule fasted (Test)/ GDC-0134 F09 capsule fasted (Reference)	F15 fasted/F09 fasted	2

9 SAMPLE SIZE JUSTIFICATION

Twenty-two healthy volunteer female subjects of non-childbearing potential who meet all the protocol inclusion criteria and none of the exclusion criteria will be enrolled into each part of the study.

If the two parts of the study are run sequentially, subjects will be encouraged to participate in both parts. The maximum number of subjects enrolled into the study will be approximately 44.

The sample size chosen for this study was based upon precedent set by other PK studies of similar nature and was not based on power calculations.

10 DEFINITION OF ANALYSIS POPULATIONS

The Safety Population will consist of all subjects who received at least 1 dose of study drug.

The **PK Population** will consist of all subjects who received at least 1 dose of study drug and have at least 1 evaluable postdose PK sample. A subject may be excluded from the PK summary statistics and statistical analysis if the subject has an AE of vomiting that occurs at or before 2 times median t_{max} .

All protocol deviations that occur during the study will be considered prior to database lock for their severity/impact and will be taken into consideration when subjects are assigned to analysis populations. Details of subject assignment to the analysis populations will be listed.

The All Subjects Population will be consistent with the Safety Population.

11 STATISTICAL METHODOLOGY

11.1 General

Data listings will be provided for the All Subjects Population. Summary statistics and statistical analyses will be performed for subjects included in the relevant analysis populations (Safety/PK).

For continuous data, summary statistics will include the arithmetic mean, arithmetic standard deviation (SD), median, minimum, maximum, and number. For log-normal data (e.g., the PK parameters: AUCs and C_{max}), the geometric mean and geometric coefficient of variation (CV) will also be presented. For categorical data, frequency counts and percentages will be presented. Data listings will be provided for all subjects up to the point of withdrawal, with any subjects excluded from the relevant population highlighted. For the calculation of summary statistics and statistical analysis, unrounded data will be used.

Missing values will not be imputed, with the possible exception of missing PK predose concentrations, as detailed in Section 11.4.2.

Data analysis will be performed using SAS® Version 9.4.

Analysis Data Model (ADaM) datasets will be prepared using Clinical Data Interchange Standards Consortium (CDISC) ADaM Version 2.1, and CDISC ADaM Implementation Guide Version 1.1. Pinnacle 21 Community Validator Version 2.2.0 will be utilized to ensure compliance with CDISC standards.

11.1.1 Definition of Baseline and Change from Baseline

Period specific baseline for each parameter is defined as the last value measured prior to dosing in each period, including repeat (vital signs and ECGs) and unscheduled (clinical laboratory parameters) readings (see Section 11.1.2 for definitions of repeat and unscheduled readings).

Mean change from period specific baseline is the mean of all individual subjects' change from baseline values. Each individual change from baseline will be calculated by subtracting the individual subject's baseline value from the value at the timepoint. The individual subject's change from baseline values will be used to calculate the mean change from baseline using a SAS procedure such as Proc Univariate.

11.1.2 Repeat and Unscheduled Readings

Repeat readings occur when the original vital signs or ECG result requires confirmation. Repeat readings are labelled as 'Repeat' in the listings and replace the original readings in all summaries and changes from baseline presentations and calculations. Prior to dosing, all readings taken in addition to the original reading are defined as predose repeats. Postdose repeat readings are defined as readings collected within 15 minutes of the actual time of the original reading. Where results are taken in triplicate and repeated, the last 3 readings are used in all subsequent calculations.

With the exception of predose results described above, unscheduled readings for vital signs or ECGs are defined as readings collected >15 minutes from the actual time of the original reading. Where results are taken in triplicate, the original reading is defined as the first reading of the triplicate. All results not taken at a scheduled timepoint for other data types (e.g., clinical laboratory parameters) are unscheduled. Unscheduled readings are labelled as 'Unscheduled' in the listings. Because unscheduled readings are not associated with any scheduled timepoint, they are excluded from all summaries (with the exception that they may be used as baseline, as stated in Section 11.1.1).

11.2 Demographics and Subject Disposition

The demographic variables age, sex, race, ethnicity, body weight, height, and body mass index will be summarized and listed by study part. Subject disposition will be summarized and listed by study part.

11.3 Prior and Concomitant Medications

Prior and concomitant medications will be coded using the World Health Organization (WHO) Drug Dictionary (Version September 2018 Enhanced Dictionary Version B3 format [or higher if version is updated during the study]). Prior and concomitant medications will be listed separately by study part.

11.4 Pharmacokinetic Assessment

11.4.1 Pharmacokinetic Analysis

The following PK parameters will be determined where possible from the plasma concentrations of GDC-0134 using non-compartmental methods performed using Phoenix WinNonlin (Certara USA, Inc., Version 6.4 or higher):

Parameter	Definition
C _{max}	maximum observed concentration
t _{max}	time to maximum observed concentration
AUC ₀₋₄₈	area under the concentration-time curve from Hour 0 to 48 hours postdose,
	calculated using the linear trapezoidal rule for increasing concentrations
	and the logarithmic rule for decreasing concentrations
AUC _{0-t}	area under the concentration-time curve from Hour 0 to the last measurable
	concentration, calculated using the linear trapezoidal rule for increasing
	concentrations and the logarithmic rule for decreasing concentrations
$AUC_{0-\infty}$	area under the concentration-time curve extrapolated to infinity, calculated
	using the formula:
	$AUC_{0-\infty} = AUC_{0-t} + (C_t/\lambda_z)$
	where C_t is the last measurable concentration and λ_z is the apparent
	terminal elimination rate constant
λ_z	apparent terminal elimination rate constant, where λ_z is the magnitude of
	the slope of the linear regression of the log concentration versus time
	profile during the terminal phase
t _{1/2}	apparent terminal elimination half-life (whenever possible),
	where $t_{1/2} = natural \log (ln) 2/\lambda_z$
CL/F	apparent systemic clearance, calculated as dose/AUC _{0-∞}
V_z/F	apparent volume of distribution during the terminal phase, calculated as
	$CL/F/\lambda_z$

The following PK parameters will be determined where possible from the urine concentrations of GDC-0134:

Parameter	Definition
A _{eu}	amount excreted in urine over a sampling interval
%F _{eu}	percentage of dose excreted in urine over a sampling interval
Total A _{eu}	cumulative amount excreted in urine
Total %F _{eu}	cumulative percentage of dose excreted in urine
CL _R	renal clearance

Additional PK parameters may be determined where appropriate.

The PK analysis will, where possible, be carried out using actual postdose times recorded in the raw data. If actual times are missing, nominal times may be used with sponsor approval.

Concentrations will be used as supplied by the analytical laboratory for PK analysis. The units of concentration and resulting PK parameters, with amount or concentration in the unit, will be presented as they are received from the analytical laboratory.

The C_{max} and t_{max} will be obtained directly from the plasma concentration-time profiles.

For multiple peaks, the highest postdose concentration will be reported as C_{max} . In the case that multiple peaks are of equal magnitude, the earliest t_{max} will be reported.

The A_{eu} for each urine collection interval will be calculated as the product of urine concentration and urine weight (assuming a specific gravity of 1 g/mL); Total A_{eu} will be calculated by summing the A_{eu} values for each collection interval over the 0-12 h, 12-24 h, 24-36 h, and 36-48 h time periods.

The $\%F_{eu}$ will be calculated for each collection interval (i) and the 0-x h time periods (Total $\%F_{eu}$) according to the following formula:

$$%F_{eu}(i) = \frac{A_{eu}(i)}{dose} \times 100$$

The CL_R will be calculated over 0-48 h according to the following formula:

$$CL_{R} = \frac{\text{Total } A_{eu \, 0-48}}{AUC_{0-48}}$$

11.4.2 Criteria for Handling Concentrations that are Missing or Below the Limit of Quantification in Pharmacokinetic Analysis

- Plasma concentration values that are below the limit of quantification (BLQ) will be set to zero, with defined exceptions as follows;
 - Any embedded BLQ value (between 2 quantifiable concentrations) and BLQ values following the last quantifiable concentration in a profile will be set to missing for the purposes of PK analysis.
 - If there are late positive concentration values following 2 BLQ concentration values in the apparent terminal phase, these values will be evaluated. If these values are considered to be anomalous, they will be set to missing.
 - If an entire concentration-time profile is BLQ, the profile will be excluded from the PK analysis.
 - If a predose concentration is missing, these values may be set to zero.
- Urine concentrations that are BLQ will be set to zero.

11.4.3 Criteria for the Calculation of an Apparent Terminal Half-Life

11.4.3.1 Number of Data Points

• At least 3 data points will be included in the regression analysis and preferably should not include C_{max} .

11.4.3.2 Goodness of Fit

- When assessing terminal elimination phases, the adjusted coefficient for determination of exponential fit (R² adjusted) will be used as a measure of the goodness of fit of the data points to the determined line.
- Regression-based parameters (i.e., λ_z , $t_{1/2}$, AUC_{0- ∞}, CL/F, V_z /F) will only be calculated if the R² adjusted value of the regression line is ≥ 0.7 .

11.4.3.3 Period of Time Estimation

- Apparent terminal elimination half-lives will be estimated over a time period of at least 2 half-lives, where possible.
- Where t_{1/2} is estimated over a time period of less than 2 half-lives, it will be flagged in the data listings at the discretion of the Pharmacokineticist, and the robustness of the value should be discussed in the study report.

11.4.3.4 Calculation of AUC

- The minimum requirement for the calculation of AUC will be the inclusion of at least 3 consecutive plasma concentrations above the lower limit of quantification, with at least 1 of these concentrations following C_{max}.
- For any partial AUC determination, nominal time will generally be used for the end of the interval. Actual times for partial AUC intervals may be used at the discretion of the Pharmacokineticist.
- The AUC_{0-∞} values (and related parameters [CL/F, V_z/F]) where the percentage extrapolation is less than 30% will be reported and included in summary and inferential statistics. Any AUC_{0-∞} values (and related parameters) where the percentage extrapolation is ≥30% will be reported but flagged and excluded from summary and inferential statistics.

11.4.3.5 Anomalous Values

- If a value is considered to be anomalous due to being inconsistent with the expected PK profile, it may be appropriate to exclude this point from the PK analysis. However, the exclusion of data must have strong justification and will be documented in the raw data and study report.
- Embedded BLQ values may be considered anomalous depending on the route of administration and the characteristics of the drug.
- Positive predose value(s) greater than 5% of C_{max} may be excluded from the summary statistics of PK tables and statistical analysis at the discretion of the Pharmacokineticist.

11.4.4 Presentation of Pharmacokinetic Data

11.4.4.1 Presentation of Pharmacokinetic Concentration Data

- The following rules will be applied if there are values that are BLQ or if there are missing values (e.g., no result [NR]) in a plasma concentration data series to be summarized.
 - For the calculation of summary statistics, BLQ values will be set to zero.
 - If an embedded BLQ value is considered anomalous within the concentration-time profile, this value will be excluded from the summary statistics.
 - Where there is NR, these will be set to missing.
 - If there are fewer than 3 values in the data series, only the minimum, maximum and number will be presented. The other summary statistics will be denoted as not calculated (NC). BLQ is considered a value.
 - If all the values are BLQ, then the arithmetic mean, arithmetic SD, median, minimum and maximum will be presented as zero, and the geometric mean and geometric CV will be denoted as NC.
 - If the value of the arithmetic mean or median is BLQ, it will be presented as zero and the geometric mean and geometric CV will be denoted as NC.

11.4.4.2 Presentation of Pharmacokinetic Parameters

- For the calculation of summary statistics of PK parameters, all NR and NC values in a data series will be set to missing.
- The AUC values will be set to NC if they have been calculated using fewer than three concentrations, and/or three concentrations if the last is C_{max} .

11.4.5 Pharmacokinetic Statistical Methodology

Descriptive statistics (mean, median, minimum, maximum, SD, geometric mean, and geometric CV) will be calculated for all PK parameters and PK concentration data.

Plasma concentrations of GDC-0134, and derived plasma PK parameters, will be listed and summarized by study part and treatment using descriptive statistics. Individual and mean concentration versus time profiles will be plotted. The primary parameters for analysis will be $AUC_{0-\infty}$ and C_{max} of GDC-0134. A linear mixed model will be applied to analyze the log-transformed primary PK parameters. The model assumes fixed effects for formulation, period, and sequence, and a random effect for subject within sequence. Estimates of geometric mean

ratios on the original scale, together with the corresponding 90% confidence intervals (CIs), will be derived for the comparisons between Test and Reference treatments. All calculations will be performed using SAS[®] version 9.4 or greater.

Example SAS code that will be used:

```
proc mixed data=xxx;
class treatment period sequence subject;
model lpk = treatment period sequence / ddfm=kr;
random intercept / subject=subject(sequence);
lsmeans treatment / diff cl alpha=0.1;
ods output lsmeans=lsmean diffs=diff;
run;
```

Within-subject CV will be calculated for $AUC_{0-\infty}$ and C_{max} based on the log-normal distribution using the following formula:

 $CV_W(\%) = [exp(mse) - 1]^{\frac{1}{2}} \times 100$

where mse is the residual error from the mixed model.

Residual plots will be produced to assess the adequacy of the model.

The parameter t_{max} will be analyzed nonparametrically using the Wilcoxon signed-rank test. Hodges-Lehmann estimates of the median difference and the corresponding 90% CIs will be calculated for comparison between test and reference treatments.

```
proc univariate data = <data in> cipctldf(alpha = 0.1);
  by parcatln parcatl pkday paramn param;
  var ref test dif;
  ods output quantiles = <data out>;
  ods output testsforlocation = <data out>;
run;
(Note: followed by the derivation of Hodges-Lehmann estimates)
```

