2.3 CLINICAL PHARMACOKINETICS OF GDC-0134

The clinical pharmacokinetics of GDC-0134 has been investigated in ongoing and completed clinical studies. As of 15 September 2018, preliminary PK data from Study GN29823 are available from 17 patients receiving escalating single oral doses of GDC-0134 and from 24 patients administered 100-1200 mg GDC-0134 QD for a planned treatment period of 28 consecutive days in the MAD stage. The PK data from completed Study GP39778 are available from 18 healthy volunteers who received 200 mg single oral doses of GDC-0134.

In Study GN29823, following a single dose, GDC-0134 was rapidly absorbed with peak concentrations achieved at around 1.5 hours (median time to maximum observed concentration $[t_{max}]$) after dosing. Biphasic elimination with a relatively rapid decline in drug concentration was observed right after t_{max} of up to 6–12 hours, followed by a slower decline of up to 168 hours. Mean apparent terminal elimination half-life ($t_{1/2}$) of GDC-0134 following a single dose was approximately 89 hours. GDC-0134 exposure in the fasted state increased with dose in an approximately dose-proportional manner across the dose range tested to date (20-640 mg).

Following multiple doses (100-1200 mg QD) of GDC-0134 in the MAD stage of Study GN29823, plasma concentrations of GDC-0134 increased with dose after a single dose and at steady state in MAD (100-1200 mg); however, the increase was less than dose proportional within the MAD dose range tested. Consistent with the long terminal elimination half-life, median accumulation following QD dosing was approximately 2 to 3-fold relative to single dose C_{max} and area under the concentration-time curve from 0 to 6 hours (AUC₀₋₆).

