	0.5	3 minutes	GDC-0134 (Plasma)
	1	5 minutes	GDC-0134 (Plasma)
	1.5	5 minutes	GDC-0134 (Plasma)
Day 1	2	10 minutes	GDC-0134 (Plasma)
	3	10 minutes	GDC-0134 (Plasma)
	4	10 minutes	GDC-0134 (Plasma)
	6	10 minutes	GDC-0134 (Plasma)
	8	10 minutes	GDC-0134 (Plasma)
	12	10 minutes	GDC-0134 (Plasma)
Day 2	24	10 minutes	GDC-0134 (Plasma)
Day 3	48	30 minutes	GDC-0134 (Plasma)
Day 5	96	6 hours	GDC-0134 (Plasma)
Day 7	144	6 hours	GDC-0134 (Plasma)
Day 15	336	6 hours	GDC-0134 (Plasma)
Day 22 ¹	504	6 hours	GDC-0134 (Plasma)

Table 7-3 Plasma Pharmacokinetic Sampling Scheme (All Study Periods)

NA = not applicable; PK = pharmacokinetic.

^{1.} The predose sample in the second period in each part (Period 2) will be used as the Day 22 PK sample for the first period in each part (Period 1).

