9.5 STATISTICAL ANALYSIS OF PHARMACOKINETIC DATA

Descriptive statistics (mean, median, minimum, maximum, standard deviation, geometric mean, and geometric coefficient of variation) will be calculated for all PK parameters and PK concentration data.

The primary parameters for analysis will be $AUC_{0-\infty}$ and C_{max} of GDC-0134. A linear mixed model will be applied to analyze the log-transformed primary PK parameters. The model assumes fixed effects for formulation, period, and sequence, and a random effect for subject within sequence. Estimates of geometric mean ratios on the original scale, together with the corresponding 90% CIs, will be derived for the comparisons between Test and Reference treatments.

Time to maximum observed concentration will be analyzed by using Wilcoxon signed-rank test, and Hodges-Lehmann estimate to generate the difference in medians between treatments (Test-Reference) and 90% CI of the median difference.

All calculations will be performed using SAS[®] version 9.4 or greater.

Specification of PK parameters for analysis; statistical level of significance to be used; criteria for study termination; procedures for accounting for missing, unused, or spurious data; procedures for reporting deviations from the original statistical plan; and selection of subjects to be included in the analyses population(s) will be presented in the Clinical Study Report and/or SAP as appropriate.

Statistical analyses details will be included in the SAP.

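### Does the unstated computing rule for the tmax Hodges-Lehmann 90% interval in SAP 11.4.5 call for a change to the plan?

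*SAP*

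**What the plan says.** Both documents plan the same nonparametric analysis. In Protocol 9.5, "Time to maximum observed concentration will be analyzed by using Wilcoxon signed-rank test", with a Hodges-Lehmann estimate and a 90% interval for the Test-minus-Reference difference. SAP 11.4.5 repeats the test and adds that "Hodges-Lehmann estimates of the median difference and the corresponding 90% CIs will be calculated for comparison between test and reference treatments".

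The code printed for tmax begins "proc univariate data = <data in> cipctldf(alpha = 0.1" and sends two things to output: quantiles and tests for location. The block closes with "Note: followed by the derivation of Hodges-Lehmann estimates". No formula, rank rule or convention for zero and tied differences appears.

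On the time basis, SAP 11.4.1 says "The PK analysis will, where possible, be carried out using actual postdose times recorded in the raw data", with one exception: "If actual times are missing, nominal times may be used with sponsor approval". Protocol 9.2 likewise bases the PK analysis on the times recorded in the eCRF.

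SAP 6.1 lists tmax as a secondary endpoint. Cmax and AUC0-∞ are primary.

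**The concern.** The one piece of interval syntax printed for tmax produces a different interval from the one the text promises. The cipctldf option gives distribution-free limits for a percentile, taken from the ordered differences themselves. A Hodges-Lehmann interval is taken from the ordered Walsh averages, that is, the averages of all pairs of differences with each difference also paired with itself. The closing note speaks of estimates and does not mention the interval. A programmer in a hurry might report the limits that the printed code delivers.

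Even a programmer who builds the right interval has choices left: exact or asymptotic ranks, and zeros kept or dropped. Sampling times are discrete, so tied and zero differences are likely if tmax is taken at scheduled times. For the primary parameters the same section prints the full mixed-model code, the degrees-of-freedom method and the CV formula, which makes the tmax part look thin. At stake would be the reproducibility of a reported interval, and possibly whether it excludes zero.

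**Working it through.** The plan states no figure for the tmax interval, so there is none to reproduce. The check is how far each open choice can move the result.

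**Inputs.** 22 subjects planned and 18 completers sought per part (Protocol 4.1); sampling times and windows from Protocol Table 7-3; median tmax about 1.5 h (Protocol 2.3: "GDC-0134 was rapidly absorbed with peak concentrations achieved at around 1.5 hours").

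**1. Rank rule.** With n differences there are M = n(n+1)/2 Walsh averages. The limits are the k-th smallest and k-th largest. The exact k comes from the signed-rank distribution. The asymptotic k is the integer part of n(n+1)/4 − 1.645·√[n(n+1)(2n+1)/24].

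- n = 18: M = 171. Exact k = 48, so the limits are the 48th and 124th (coverage 90.1%). Asymptotic: 85.5 − 1.645 × 22.96 = 47.73, so k = 47.
- n = 22: M = 253. Exact k = 76, so the limits are the 76th and 178th (coverage 90.2%). Asymptotic: 126.5 − 1.645 × 30.80 = 75.83, so k = 75.

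The two rules differ by one rank. In simulation that is about 1-4% of the width.

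**2. Zeros, worst case.** Take 18 differences on scheduled times, in hours: −1 once, −0.5 three times, 0 five times, 0.5 five times, 1 twice, 1.5 once, 2 once.

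| Rule | Estimate (h) | 90% interval (h) |
|---|---|---|
| All 171 Walsh averages, ranks 48 and 124 | 0.25 | 0.00 to 0.50 |
| Zeros dropped, n = 13, ranks 22 and 70 of 91 | 0.50 | 0.00 to 0.75 |
| Order statistics 6 and 13 of the 18 differences | not applicable | 0.00 to 0.50 |

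Using rank 47 in place of 48 leaves the first row unchanged. The example has 5/18 = 28% zeros because it uses scheduled times, which is not the planned basis.

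**3. Zeros on the planned basis.** The simulations assume log-normal tmax with median 1.5 h, or 3.0 h for a later peak with food; between-subject log-SD 0.3; within-subject log-SD 0.3, 0.4 or 0.6; no period effect; and sampling deviations, rounded to the minute, over 20% or 100% of the Table 7-3 windows. Only the 1.5 h and the windows come from the documents.

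- Exact zeros: 1-12% of differences on actual times, against 17-35% on scheduled times.
- At n = 18 with no true shift, on actual times, dropping zeros widens the interval by about 2-10 minutes, on widths of 0.6-2.4 h, and moves the estimate by about 0.5-3 minutes.
- Over n = 18, 20 and 22 the widening on actual times is about 2-22%.
- Keeping or dropping zeros changes whether the interval excludes zero in 0-2% of trials on actual times, even with an assumed shift of one third of the median tmax.
- Coverage of the exact-rank interval with zeros kept is 89-95% on actual times.

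**4. The printed limits used by mistake.** For continuous differences, order statistics 6 and 13 at n = 18 have coverage Σ C(18,x)/2¹⁸ over x = 6 to 12, which is 90.4%. At n = 22 the pair 8-16 gives 90.7% and the pair 7-16 gives 94.8%. Mean width relative to the Hodges-Lehmann interval is −1% to +6% at n = 18. At n = 22 it is +2% to +11% (8-16) or +19% to +28% (7-16). These limits would be valid, and at n = 22 somewhat wide. At n = 18 they would disagree with the Hodges-Lehmann interval on excluding zero in about 1-8% of trials with no shift, and in 19-26% with the assumed shift.

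**5. What depends on it.** Neither document attaches a decision to the tmax interval, and nothing computed for AUC0-∞ or Cmax uses it.

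**The case for a change.** The best argument for a change is that Protocol 9.5 leaves analysis details to the SAP, and the SAP must be final before database lock. One sentence now would remove a choice that could otherwise be made with the data in view. The choice does change printed numbers: in the worked example the estimate doubles from 0.25 to 0.50 h when zeros are dropped. Mistaking the printed limits for the promised interval does not depend on zeros at all, so actual times do not cure it.

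Part of this stands. The rank rule and the zero and tie convention are not written down, and writing them down would cost almost nothing.

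The rest is weaker. The doubling belongs to scheduled times, which the SAP allows only where an actual time is missing. The 19-26% disagreement measures a substitution that the SAP does not announce. Its text ties the interval to the Hodges-Lehmann estimate, and its note places that derivation after the printed step, so the block is openly not the whole computation. The block also supplies the signed-rank test, which explains why it is there. The SAP refers to table, figure and listing shells that are not available here. They may or may not hold more detail, and the conclusion does not rest on them.

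**Conclusion.** No change to the plan follows. The omission is real but small: a computing convention is left to the analysts, and the analysis itself is neither wrong nor missing. The method, the confidence level, the direction of the difference and the time basis are all fixed. What is left open is one rank in 171 or 253 and the treatment of a small share of zero differences. Each way of filling the gap gives a usable interval for a descriptive secondary endpoint, in a study whose SAP calls it hypothesis-generating.

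On the planned time basis the zero convention is worth about 2-10 minutes of interval width and up to about 3 minutes in the estimate at 18 subjects. Those figures rest on assumed tmax distributions and sampling deviations. The rank figures are exact and need no such assumption. The conclusion would be less comfortable if many actual times were missing and scheduled times replaced them, or if a decision were attached to the tmax interval. The plan provides for the first only as an exception and does not do the second.
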